**Phosphodiesterase Type 5 Inhibition to Improve
Endothelial Function and Vascular Remodeling in
Chronic Kidney Disease and End Stage Renal Disease
Patients Requiring New Arteriovenous Fistula
Study Protocol and Statistical Analysis Plan**

NCT Number: NCT02414204

July 11, 2018

[name], Principal Investigator
University of Alabama at Birmingham
Birmingham, AL 35294

“Phosphodiesterase Type 5 Inhibition to Improve Endothelial Function and Vascular Remodeling in Chronic Kidney Disease and End Stage Renal Disease Patients Requiring New Arteriovenous Fistula”.

PI: [name]., M.S.P.H, F.A.C.P., F.A.S.N.
Associate Professor of Medicine
Department of Medicine/ Division of Nephrology
Mailing address: [name]
[contact]
[contact]
Email: [contact]

Protocol Version: 1.0

Protocol Date: 2-5-15

Protocol

1. Background:

The vascular access is the “Achilles Heel” of the hemodialysis procedure. 60% of arteriovenous fistulas (AVFs) created fail to mature adequately for hemodialysis (AVF non-maturation), due to a combination of early aggressive venous neointimal hyperplasia development and inadequate vasodilation (adverse remodeling). At present, there are no effective therapies to treat vascular access dysfunction. The treatment paradigms to date have focused on delivery of therapies post-AVF creation and most recently at the time of surgery. Preliminary data from the Hemodialysis Fistula Maturation (HFM) consortium suggests that profound endothelial dysfunction, as measured by flow-mediated (FMD) and nitroglycerin-mediated (NMD) in the brachial artery, is present in the large majority of patients prior to AVF creation. This suggests that the vascular health of the vessels at the time of AVF creation may play an important role in AVF non-maturation. Furthermore, the period immediately after AVF creation is important because the blood vessels are adjusting to new hemodynamic parameters. There are no previously published studies addressing therapies to modify or improve endothelial function prior to and after vascular access creation. Sildenafil, a phosphodiesterase 5 inhibitor that enhances the effects of nitric oxide (NO), has been shown in experimental and clinical studies in cardiovascular disease to improve endothelial function and decrease vascular stenosis. Therapies to enhance endothelial function, through NO production, have not been evaluated in vascular access dysfunction to date and may be beneficial in AVF maturation.

2. Recruitment Population:

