Sildenafil 20mg twice a day or placebo twice a day, based on randomization scheme. Subjects will begin either placebo or Sildenafil after randomization during the first vascular function visit until the 2 weeks postoperative arteriovenous fistula ultrasound.

Enrolled subjects will have an initial brachial artery flow-mediated dilation (FMD) and venous plethysmography (VP) studies performed approximately 2 weeks prior to scheduled AVF creation and a subsequent FMD and VP study prior to surgery. The FMD and VP studies are non-invasive studies. Completion of these studies will take approximately 3-4 hours.

Up to four teaspoons of blood will be drawn at the 1st FMD/VP study prior and second FMD/VP study. Blood samples will be obtained using the standard method used to obtain blood for routine hospital tests. Completion of blood draw will take approximately 10-15 minutes.

Pre-operative, 2 weeks and 6 weeks post-operative ultrasounds will be performed on participants. The pre-operative and 6 week ultrasounds are part of standard medical care and will be performed whether the participant is in the study or not.

Discarded vein and artery specimens (approximately 5-10 mm each) will be collected at the time of AVF surgery. This procedure requires 3-5 minutes, and does not affect surgical outcome.

A total of 21 subjects will be recruited for this study with prospective follow-up. The first patient will be unblinded and receive the drug. Subsequently, 10 subjects will be randomized to receive 20 mg of Sildenafil twice a day oral and 10 patients randomized to receive placebo twice a day oral. Information related to demographics, comorbidities, and AVF outcome following surgery will be collected. The primary clinical endpoint is change in baseline and 2 week FMD/VP measurements. The secondary outcome is change in blood flow and vein and artery diameters at 2 and 6 weeks.

Study Visits:

Visit 1: Screening and enrollment 1-2 hours (Research)

- Informed consent
- The study team will determine qualification to participate in this study

Visit 2: Baseline Visit (in some cases Visit 1 and 2 could be combined) (Research)

- Detailed medical history
- Height and weight measured
- Blood draw (in some cases this could occur in the dialysis unit)

Visit 3: 1st Vascular Function Test and Pre-operative Ultrasound

- Vascular Ultrasound (Standard care)
- Vascular Function Testing (3-4 hours)
 - Brachial artery flow mediated vasodilation and venous plethysmography (Research)

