July 11, 2018

[name], Principal Investigator
University of Alabama at Birmingham
Birmingham, AL 35294

The data will be analyzed in two stages: (1) descriptive statistics, which will include means and standard deviations for normally distributed continuous variables, medians and interquartile ranges for skewed continuous variables, and proportions for categorical measures and (2) two-group t test, Wilcoxon rank-sum tests, chi-square tests, and simple logistic regression and multiple logistic regression modeling. P values <0.05 will be considered statistically significant.

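### The SAP's chi-square test, version unstated, is a poor choice for binary comparisons between arms of 10: uncorrected it can exceed 5% after one loss, corrected it runs at 1-2% (minor, because no named endpoint is binary)

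*Combined protocol and SAP*

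**What the plan says.** The SAP's analysis text is a single paragraph. Its inferential stage consists of "two-group t test, Wilcoxon rank-sum tests, chi-square tests, and simple logistic regression and multiple logistic regression modeling", followed by "P values <0.05 will be considered statistically significant". It does not say whether the continuity correction is applied, gives no exact or small-sample alternative, and assigns no test to any outcome.

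The arm sizes are in protocol section 5 (Study Procedures): "10 subjects will be randomized to receive 20 mg of Sildenafil twice a day oral and 10 patients randomized to receive placebo". The same paragraph says "A total of 21 subjects will be recruited for this study with prospective follow-up". The twenty-first person is the first subject, who receives sildenafil without randomisation. The documents do not say whether that person enters the comparison.

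On endpoints, section 5 states "The primary clinical endpoint is change in baseline and 2 week FMD/VP measurements". The secondary outcome is change in blood flow and vessel diameters. Both are continuous. The fistula outcome appears only as collected data: "Information related to demographics, comorbidities, and AVF outcome following surgery will be collected". Section 6 adds two years of follow-up for fistula survival. The only event rate in the documents is in section 1 (Background): "60% of arteriovenous fistulas (AVFs) created fail to mature adequately for hemodialysis".

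**The concern.** Chi-square relies on a large-sample approximation. With 10 per arm and a 60% event rate, the expected counts are 6 and 4, and 4 is below the usual guide of 5. At this size the two common forms of the test can disagree on the same table, and the error rate of the uncorrected form moves when a patient or two is missing.

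Fistula failure is the clinical problem that motivates the trial, so a failed-versus-matured comparison is a natural use of the listed methods. A result quoted at P<0.05 could then carry a true error rate somewhat above 5%, or come from a test that discards much of the little power available. A software default and the final arm sizes would decide which.

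**Working it through.** **Inputs.** Threshold 0.05 (SAP). Arms 10 and 10 (section 5). Event rate 60% (section 1; a background figure, not a design assumption). The documents contain no sample-size or power calculation, so there is no figure of the plan's own to reproduce. Lost patients are an assumption, shown as a range.

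**Expected counts at 10:10.** 10 × 0.60 = 6 failures and 10 × 0.40 = 4 non-failures per arm.

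**Example table: 2/10 versus 7/10 failures.** With cells a=2, b=8, c=7, d=3, |ad − bc| = |6 − 56| = 50. The margins are 10, 10, 9 and 11, and N = 20.
- Uncorrected: 20 × 50² / (10 × 10 × 9 × 11) = 50,000/9,900 = 5.05; P = 0.025.
- Corrected: 20 × (50 − 10)² / 9,900 = 32,000/9,900 = 3.23; P = 0.072.
- Boschloo, with the arm sizes fixed at 10 and 10: P = 0.041.
- Simple logistic regression on arm: Wald P = 0.033, likelihood-ratio P = 0.021.

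The unstated correction decides significance for this table.

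**True error rate.** For arms n and m with common failure rate p, size(p) = Σ Bin(x; n, p) × Bin(y; m, p) over all tables (x, y) that the test rejects. All tables were enumerated and the sum maximised over p. Entries are percentages.

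| Arms | How it could arise | Uncorrected, maximum | Uncorrected, p = 60% | Corrected, maximum | Boschloo, maximum |
|---|---|---|---|---|---|
| 10:10 | as planned | 4.22 | 4.03 | 1.28 | 4.22 |
| 10:9 | one lost | 6.47 | 6.25 | 1.92 | 3.64 |
| 9:9 | one lost in each arm | 5.70 | 5.46 | 1.00 | 3.28 |
| 10:8 | two lost in one arm | 5.31 | 4.97 | 1.70 | 4.61 |
| 8:8 | two lost in each arm | 7.68 | 7.06 | 2.13 | 2.79 |
| 11:10 | first subject included | 6.35 | 6.21 | 2.03 | 4.05 |

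The size also depends on the event rate. At p = 10% and 10:10 it is 0.9% uncorrected and 0.1% corrected.

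**Power.** The same sum with different rates in the two arms, at 10:10:
- 60% versus 10% failure: corrected 47%, uncorrected 66%, Boschloo 66%.
- 60% versus 20% failure: corrected 25%, uncorrected 42%, Boschloo 42%.

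At 10:10, Boschloo and uncorrected chi-square reject exactly the same tables. At 9:9, for 60% versus 10%, the sum gives 68% for uncorrected chi-square and 58% for Boschloo. Part of that gap reflects the uncorrected test running above 5%.

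**Logistic regression.** With arm as the only covariate, the likelihood-ratio test is the likelihood-ratio chi-square. Its maximum size is 8.76% at 10:10 with nobody lost (5.97% at p = 60%). Changing the chi-square wording alone would leave this second P value in the plan.

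**The case against.** The strongest reply is that no named endpoint uses this test. The primary and secondary endpoints are continuous and fall to the t test or the Wilcoxon test. The fistula outcome is not defined as binary, given a time point, called an endpoint or assigned a test, and the chi-square tests may be meant only for baseline characteristics. This stands, and it is why the point is minor.

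A second reply is that the ordinary uncorrected test holds 5% at the planned 10:10 and has the same power there as Boschloo. This also stands. The problem needs one of three further conditions: a missing outcome, inclusion of the first subject, or the corrected form. None is far-fetched with two years of fistula follow-up, 21 recruits and no version named, but none is stated to occur.

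A third reply is that preferring Boschloo is a matter of taste, since Fisher's test also controls error. That is partly right: Fisher's test would be acceptable for error control. At 10:10, however, its maximum size is 1.28% and its power for 60% versus 10% is 47%, the same as corrected chi-square.

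A reader might infer that chi-square is the only two-arm method listed for binary data. It is not, because simple logistic regression also compares two arms.

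**Conclusion.** The point holds as a minor one. For binary comparisons the stated method is either slightly liberal once the arms are no longer 10:10, or needlessly weak if corrected. With one or two patients lost in total, the maximum size of the uncorrected test is 5.3% to 6.5%; it is about 6.4% if the first subject is added. The corrected form stays at about 1-2% and gives up 19 points of power at 10:10 for 60% versus 10% (66 − 47).

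These figures rest on assumed losses, on the fistula outcome being analysed as failed or not, and on maximising over the event rate.

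A reader might infer that one or two drop-outs push the error to about 8%. The calculations do not support this: 7.7% needs two lost in each arm and a true rate near 50%. The likelihood-ratio form can exceed 8%, but the SAP does not name it. A reader might also infer that the trial's main conclusion is exposed. It is not, because the primary comparison does not use chi-square.

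**What to change.** In the SAP, replace the chi-square entry with text such as: *Two-arm comparisons of binary variables will use Boschloo's exact unconditional test; variables with more than two categories will use the Fisher-Freeman-Halton exact test; both at P<0.05. These tests give the between-arm P value. Logistic regression will be used for estimates only, and its Wald or likelihood-ratio P values will not be used for the between-arm comparison.*

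Boschloo's maximum size is below 5% at every arm size tabulated, and at 10:10 nothing is lost against uncorrected chi-square. The cost is a sentence or two in the SAP, with no new data and no change in sample size; the test is available in standard software. The downside is lower nominal power than uncorrected chi-square when patients are lost, as in the 9:9 comparison above.
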